Protocol Title page

NCT number: NCT03428815

Official Title: Effects of Temperature Control Liner Materials on Long-Term Outcomes of Prosthesis Use

Document Date: January 15, 2020

The protocol has been approved by the responsible Institutional Review Boards. Study subjects are asked by the principle investigators to provide informed consent in accordance with human-subjects protection regulations.

**Subjects:** Subjects are recruited from the community at two sites, in Chester, PA, and Pittsburgh, PA. Inclusion criteria are the use of a prosthesis with liner suspension, at least one year of prosthesis use, a well-fitting socket, the ability to walk with the prosthesis outdoors without notable limitations (K-Level 3), stable weight, and absence of acute medical conditions that would temporarily affect the ability to use prostheses. Exclusion criteria are use of a non-standard liner size, known allergies against liner materials, and any inability to understand the protocol and to comply with the associated tasks, such as maintaining a log of days when the prosthesis could not be used.

Power analysis was based on the cross-over statistical methods above and previous literature and One-sided determination. Halsne, et al. , in an analysis of 12-month step activity data in participants with trans-femoral amputation reported that the average change in step activity scores for subjects in the hot and cold months of the year was significantly higher than in the moderate temperature months of the year corresponding to an effect size of 0.47. This effect size and a sample size of 50 subjects, results in 85% power to detect significant differences.

The assumed effect size would equate a difference in prosthesis utilization of four days per year if the average yearly number of days with prosthesis use has a standard deviation of 10 days. Irrespective of the statistical significance of such an effect, every day of work absence has a relevant economical effect to the employee and the employer. Given the duration of the study and the potential reluctance of subjects to change their liner type, it is anticipated that up to 9

subjects (18%) do not complete the protocol, bringing the statistical power to 80%. Comparable prospective intervention studies in the past have utilized sample sizes between nine and 20.

A steady state within either of the interventions will be assumed, yet it will be possible to detect any baseline drift or seasonal fluctuations with the proposed repeated measures design. Previous studies have used a repeated measures design to investigate the reliability of outcome measures, such as the Locomotor Capabilities Index and the Two-Minute-Walk test. The Prosthesis Evaluation Questionnaire (PEQ) has been validated in that fashion as well.

Missing values are possible due to drop-out and intermittent non-compliance with the data collection schedule. This would not invalidate “year-on-year” comparison of the remaining data sets. Provided that baseline characteristics can be sufficiently described by existing data, it may also be possible to interpolate and extrapolate missing data points with some accuracy.

Despite the long duration of the data collection, the intervention itself will have a comparably low burden on the subjects’ daily lives, which is expected to make participation appealing to a wide range of potential subjects who are targeted by online and offline postings.

**Methods:** The protocol utilizes a double-blind longitudinal cross-over research design. A sample of trans-tibial prosthesis users is randomly assigned to one of two groups. While subjects in one group receive PCM liners, the members of the other group are fitted with regular gel or silicone liners. After six months, the first group receives conventional liners (and turn their PCM liners in) and the second group receives PCM liners (Table 1). Prostheses in either group are equipped with activity monitors, and participants are asked to keep daily notes of any perceived issues with their residual limb or socket fit. In regular intervals, subjects’ physical performance capabilities and prosthesis-related quality of life, including limb and overall health, is assessed using standardized methods.

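### The power paragraph presents two different effect sizes as one (0.47, and four days at SD 10, which is 0.40), and 85%/80% power does not follow from 0.47 on the basis given

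*Combined protocol and SAP*

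**What the plan says.** All the power text stands in the Subjects section of the combined protocol and SAP.

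- **Basis:** "Power analysis was based on the cross-over statistical methods above" together with "previous literature and One-sided determination".
- **Effect:** taken from a published 12-month step-activity analysis, "corresponding to an effect size of 0.47".
- **Power:** "This effect size and a sample size of 50 subjects, results in 85% power to detect significant differences". Up to nine of the 50 subjects (18%) are expected to "do not complete the protocol, bringing the statistical power to 80" percent.
- **Effect in days:** "The assumed effect size would equate a difference in prosthesis utilization of four days per year". This is conditional on an SD of 10 days for the number of days of use in a year.

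The Methods section confirms a two-period cross-over with six months per liner: "After six months, the first group receives conventional liners", and the other group changes the opposite way. Statistical Plan and Data Analysis describes mixed-effects models and a Benjamini-Hochberg adjustment. Neither section gives an alpha, a sidedness for the test, the scale of the 0.47, a within-subject correlation or an SD of the within-subject difference.

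**The concern.** Two things do not fit. First, the paragraph treats 0.47 and four days at SD 10 as the same effect, and a simple division shows that they are not. Second, 0.47 is a fairly large effect for a paired comparison of 50 people tested one-sided, so 85% looks too low on that reading.

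These sentences are the quantitative justification for 50 subjects. If the effect, its scale and the alpha cannot be identified, a reader cannot say what difference the trial was designed to detect, and cannot judge a null result against a claim of 80% power.

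**Working it through.** **Inputs from the Subjects section:** effect 0.47; n = 50; up to 9 non-completers; stated power 85% and 80%; one-sided; cross-over; four days per year; SD 10 days.

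**Assumed, because not stated:** alpha (one-sided 5%, with other values tried) and the scale of the effect (both usual scales tried). The case n = 41 takes all nine non-completers as giving no data.

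**Step 1. Attrition.** 9/50 = 18%, and 50 − 9 = 41. This agrees with the plan.

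**Step 2. Effect in days.** 4/10 = 0.40. Conversely, 0.47 × 10 = 4.7 days, and four days would equal 0.47 only if the SD were 4/0.47 = 8.5 days. This step needs no alpha or correlation.

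**Step 3. Trying to reproduce 85%/80% from 0.47 as a paired effect.** Power = P(T > t₁₋α), where T is noncentral t with n − 2 degrees of freedom and noncentrality d√n. For n = 50 the noncentrality is 0.47 × √50 = 3.32; for n = 41 it is 0.47 × √41 = 3.01.

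| One-sided alpha | n = 50 | n = 41 |
|---|---|---|
| 10% | 97.8% | 95.5% |
| 5% | 94.9% | 90.5% |
| 2.5% (two-sided 5%) | 90.3% | 83.5% |
| 1% | 81.7% | 71.8% |
| Plan | 85% | 80% |

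No row matches. Reaching 85% at 50 needs a one-sided alpha of about 1.4%; reaching 80% at 41 needs about 1.9%. So no single alpha gives both figures exactly, and neither value is a usual choice. Using n − 1 degrees of freedom changes nothing material.

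**Step 4. The plan's four days over SD 10, as a paired effect.** d = 0.40, noncentrality 0.40 × √50 = 2.83 and 0.40 × √41 = 2.56. At one-sided 5%, power is 87.4% and 80.8%, which is 2.4 and 0.8 points above the stated figures. At one-sided 2.5% it is 79.2% and 70.5%.

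**Step 5. 0.47 on the between-subject SD scale.** With equal period variances and within-subject correlation ρ, the paired effect is d = 0.47/√(2(1 − ρ)). At one-sided 5%:

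| ρ | d | n = 50 | n = 41 |
|---|---|---|---|
| 0 | 0.332 | 74.9% | 67.2% |
| 0.25 | 0.384 | 84.9% | 77.9% |
| 0.30 | 0.397 | 86.9% | 80.3% |
| 0.50 | 0.470 | 94.9% | 90.5% |
| 0.70 | 0.607 | 99.5% | 98.5% |

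A correlation of about 0.25 to 0.30 comes close to both stated figures. At ρ = 0.50 this scale and the paired scale coincide.

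**The case against.** The strongest reply is that power cannot be computed from an incomplete set of inputs, so a mismatch on one chosen reading proves no error. The only SD in the paragraph is that of the yearly number of days of use. That looks like a between-subject SD and points away from the paired reading. On the between-subject scale one undeclared correlation recovers both figures: ρ = 0.28 gives d = 0.392 and power of 86.1% and 79.4%. The sentence in days is also conditional and illustrative, and the reference to methods above may only reflect the order of the text.

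Much of this stands. It rules out three stronger inferences that a reader might draw:

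- **That the true power is about 95% and 90%, so the trial is larger than it needs to be.** This holds only if 0.47 is standardised by the SD of within-subject differences, which the documents do not say.
- **That the trial is underpowered.** Some readings fall below 80% and others rise well above 85%; the documents do not choose between them.
- **That the four-day effect is not the one powered.** A paired effect of 0.40 at one-sided 5% lies close to the stated pair, so it may well be. Closeness does not prove it, since Step 5 comes as close.

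The reply does not remove the contradiction between 0.47 and 0.40. Truncating 4.7 to four is not ordinary rounding, which would give five. On the paired reading at one-sided 5%, the difference is worth 94.9 − 87.4 = 7.5 points of power at 50 subjects and 90.5 − 80.8 = 9.7 points at 41. Nor does the reply supply the missing inputs: the later sections on design and analysis do not contain them.

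**Conclusion.** The point holds in two parts.

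1. The power paragraph contradicts itself on the effect size: 0.47 against 0.40, or 4.7 days against four. This is certain and rests on the plan's own numbers.
2. The stated 85% and 80% do not follow from 0.47 with the cross-over, one-sided basis given. As a paired effect, 0.47 misses by about 10 points at one-sided 5% (94.9% and 90.5%), and by 5.3 and 3.5 points at one-sided 2.5% (90.3% and 83.5%). Both alphas are assumptions.

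Two routes approach the stated pair, and the documents do not say which, if either, was used. One replaces 0.47 by 0.40; the other needs a correlation that the plan does not give. The supportable conclusion is that the powered effect cannot be identified. Whether actual power is above or below the stated figures remains open. The correction should be made, but it is one of reporting and consistency and not a flaw in the design.

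**What to change.** In the Subjects section:

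- Use one effect size throughout: either 0.47 with 4.7 days, or 0.40 with four days, at SD 10.
- State alpha and sidedness, and give the same sidedness in Statistical Plan and Data Analysis.
- Say whether the effect is standardised by the between-subject SD or by the SD of the within-subject difference. Give that SD or the within-subject correlation; if it is unknown, show power over a range. Since each liner is worn for six months, say also whether the SD of 10 days is for a year or for a six-month period.
- Replace 85% and 80% with the power those inputs yield at 50 and 41 subjects, or keep them if the declared inputs support them.
- If a fuller power calculation exists elsewhere, copy its inputs in, and correct the reference to methods above.

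The cost is a short recalculation and a few revised sentences. No change to sample size or outcomes is needed. The downside is that the restated power may be less favourable than 85% and 80%.

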**Table 1: Schedule of enrolment, interventions, and assessments**

	STUDY PERIOD					
	Enrolment	Allocation	Post-allocation			Close-out
TIMEPOINT	$-t_1$	Jan 15 or Jul 15	Every 6 weeks	6 months	12 months	12 months
ENROLMENT:						
Eligibility screen	X					
Informed consent	X					
Liner size determination	X					
Allocation		X				
INTERVENTIONS (Randomized sequence):						
PCM liner			↔			
Placebo liner				↔		
ASSESSMENTS:						
Demographics, Anthropometrics	X					
Two minute walk (2MWT) distance			X			X
PEQ Scores			X			X
StepWatch activity data			X			X

Comparing liners over the duration of six months allows detecting short- and long-term effects of the different approaches, including effects due to seasonal outdoor temperature changes, material abrasion and fatigue, and potential unsustainable material properties (i.e., diminished temperature control capabilities of the PCM). In order to cover a comparable portion of the year regarding climatic conditions, the protocol is started at one of two dates only: Mid-Winter (around January 15th) or Mid-Summer (around July 15th). Any possible washout period after changing liners is expected to be completed well within the first assessment intervals , so that unbiased data can be compared for all the listed assessment points for either liner.

Randomization is performed by the study statistician, using proc survey select available in SAS version 9.4. in a block randomization scheme with lengths of 2 and 4. Blocks length is unknown to the clinical personnel. This block design assures a balanced allocation in the groups and reduces the chance that testing personnel will be able to guess the next intervention group assignment. This, in turn, serves to minimize bias in participant allocation to the intervention group at the beginning of the study.

Upon entering the study, every subject receives two identical new liners that match their currently used one in size as measured by a credentialed prosthetist. The liner material is either the same as in their existing liner or PCM infused silicon, depending on group allocation. In order to blind the subjects and study personnel to the treatment, all study liners are custom ordered for each subject from the same manufacturer (Willowood, Sterling, OH) in a uniform color and outer fabric design. The packaging is uniform as well apart from a label containing the study participant number provided at ordering. Every liner is imprinted with a unique serial number that is the only sign by which it can be identified as a PCM or conventional liner. The manufacturer provides a list of these numbers, which will only be accessed by research personnel

once the data collection and analysis procedures are completed, so that the results can be attributed to the proper group. Two identical liners are provided to allow subjects to alternate between them on a daily basis, which is recommended practice in order to allow cleaning and air drying liners and to maximize life time of the material. (A regular life time of six months continuous wear is common for prosthesis liners.) Subjects are instructed to handle and rotate the liners in their usual way, in order to assure realistic test conditions, but are asked to not wear their previously existing liner for the duration of the study.

The prosthesis-related quality of life is assessed during this first appointment, using domains “About the prosthesis” (question group 1 of the PEQ), “Specific Bodily Sensations” (group 2), “Ability to Move Around” (group 4), and “Satisfaction with particular Situations” (group 5). “Importance of different aspects” (group 7) is assessed as well, to provide insights for appropriate interpretation of responses. The PEQ contains a large number of questions that have been devised to cover all aspects of prosthesis-related quality of life. The explicit intention of the tool is to provide the option of customizing a questionnaire by selecting a subset of the PEQ questions, all of which are considered equivalent and are scored on an analog scale from 0 to 100. The PEQ is valid for lower-limb prosthesis users, has high internal consistency (Cronbach’s alpha = .73 – .89) and temporal stability over a mean retest period of 30 days (ICC = .79 – 90). The likewise administered two-minute walk test (2MWT) has well established psychometric properties in lower-limb prosthesis users. Of particular interest to the proposed study is the responsiveness of the 2MWT to rehabilitation in lower-limb prosthesis users. Significant increases in total distance were found from initial prosthesis fitting (baseline) to discharge from rehabilitation, and at a 3-month follow-up. A Stepwatch monitor (Modus Health, Washington, DC) is affixed to the ankle of the prosthesis and measure step counts over time.

This device has been utilized for a large number of research studies involving lower limb prosthetics and meets the specifications issued by the Department of Veterans Affairs regarding outcome assessment technology. Using the “Trex” evaluation algorithm, the device allows an assessment of user activity by considering ambulation energy, peak performance, and cadence variability indices.

In addition to determining liner sizes, subjects’ height, weight, age, and time since limb loss are recorded at the first appointment.

Subjects are asked to continue their regular activities of daily life while wearing the new liner, and to make a note of any days during which the prosthesis could not be used due to residual limb health issues, as a redundancy to the step counter data. About every two weeks, a member of the research team will schedule a 5-minute appointment with the subject to read out Stepwatch data. Subjects are not required to come to the research site for the respective appointments, which may be scheduled at their homes or places of work according to subjects’ preferences. While the Stepwatch monitor can store up to 50 days of data, two-week-intervals have been chosen to mitigate the adverse effects of possible equipment malfunction or application errors. Any adverse events or other unsolicited reports will be recorded as they occur.

Every six weeks, appointments are scheduled to conduct the 2MWT, complete sections “About the prosthesis”, “Specific Bodily Sensations”, “Ability to Move Around”, “Satisfaction with particular Situations”, and “Importance of different aspects” of the PEQ, and read out step data.

At the 6-month appointment, after completing 2MWT and PEQ, subjects turn in their two study liners and receive two new liners, representing the respectively other variety. Following a short rest, subjects will complete the 2MWT and PEQ once more before the test day is concluded while wearing the new liner.

The 12-month appointment marks the end of the data collection for this study. Individuals blinded to liner type will perform all data collection.

Subjects receive a compensation of \$30 per site visit for a total compensation of \$270. This payment schedule is intended to reduce the occurrence of drop-outs.

***Outcome Variables:*** The main outcome variable is prosthesis utilization and is operationally defined as “total step count per time” and as the “number of days with prosthesis use per time”. Prosthesis utilization is the clinically most relevant variable, as it describes the extent to which a person’s limb loss affects their social and economic participation. To determine the number of days of prosthesis use, self-reported information will be evaluated along with step count data. A day without substantial prosthesis use will be assumed if the daily step count is below the 20th percentile for the average daily step count of the respective individual over the full year. Only if both methods agree on the number of dates without prosthesis will the information be used for analysis in order to reduce the errors caused by inaccurate memory or by malfunctioning equipment.

Secondary outcome variables will be “Step count bouts per time unit”, “Two-minute walk distance”, “Prosthesis function rating”, “Well-being rating”, “Mobility rating”, and “Satisfaction rating”, the latter four of which are based on question groups 1, 2, 4, and 5 of the PEQ respectively. Analyzing those variables will allow a more comprehensive understanding of the effects of PCM liners and may inform the hypotheses of subsequent studies investigating their function mechanisms.

Depending on the eventual sample composition, it may be possible to extract incidental findings on the effects of demographic and anthropometric factors on measured outcomes with the

different liners. Any such results may be useful as pilot data for subsequent studies to further investigate the utility of PCM in prosthetics.

Several possible comparison variables are deliberately not included in this clinical trial.

Monitoring changes in liner temperature or material properties during use would necessitate the use of additional data collection equipment, which would be likely to interfere with the regular use of the liners and thus pose a bias to the measured data. Also, it is unclear how temperature data should be interpreted (e.g., whether lower temperatures are always better than higher, or steady temperatures better than fluctuating) to become clinically meaningful. It is anticipated that the findings of the present study motivate subsequent research to investigate the function mechanisms of PCM liners and to better explain the results of this study.

Skin health, although an important outcome of prosthesis use, has likewise not been included in the study protocol. Assessment of residual limb skin health may help detect a number of adverse reactions to prosthesis use, ranging from skin abrasion to tissue necrosis. Measuring skin health outcomes results is fairly subjective and requires timely notification and assessment as skin issues occur. It is thus challenging to apply a reliable measure consistently across time, and especially across different research sites. This study focuses on prosthesis utilization, and considers skin and other health issue to have effects on the measured quality and quantity of prosthesis utilization. For the purposes of this research, the mechanisms that may lead to changes in that outcome variable are not the focus, and investigating them is therefore deferred to subsequent studies.

***Statistical Plan and Data Analysis:*** Exploratory data analysis will be conducted prior to formal statistical analysis. The distributions of all key variables will be examined to check for data errors and ensure that modeling assumptions are not violated. Numerical summaries including

means, standard deviations, medians and histogram graphical techniques will be used for continuous variables and frequencies will be computed for categorical variables.

Patterns of association between descriptive measures (i.e., demographic and diagnosis characteristics) and intervention outcomes will be examined using paired t-tests, chi-square tests with Fisher's exact, correlation analyses (and regression analyses, as appropriate). From these analyses, critical demographic and clinical characteristics will be identified that will be controlled for in the statistical models and incorporated into the design of future controlled clinical studies. Data will be analyzed according to study group membership regardless of study completion. However, missing data patterns will be examined and reasons described for attrition and missing data because such patterns may be informative for identifying systematic biases in future studies. The Kolmogorov-Smirnov test will be used to verify the normality assumption and if it is violated appropriate transformations will be considered. Correction for multiple testing will be by adjusting p-values using the Benjamini-Hochberg method. Prior to formal statistical analysis, data will be compared across treatments to check if they are comparable. If differences exist, baseline demographic effects will be taken into account in mixed effects models. The correlation among repeated measures will be examined and adjusted appropriately such as unstructured, confound symmetry, or auto-regressive.

Outcome data are collected at baseline, 1.5-month, 3-month, 4.5-month, and 6 months and repeated at the 2nd half-year. The effect of intervention, time, and group\*time interactions will be evaluated. Baseline data for key variables will be compared between randomization groups, and if they are different, a random intercept mixed effect will be used. Mixed effects modeling techniques will be used for the repeated measures. Since mixed effects models do not assume a balanced design, subjects who do not have data (dropouts) on all 10 time points will still be

included in the analysis (intent to treat). It will be tested if scores for the intervention are significantly different from the control condition's scores.

Possible additional analyses include a more detailed investigation of prosthesis utilization over time by comparing seasons, months, weekdays, or hours of day within and across interventions. Furthermore, it may be possible to analyze covariates that predict prosthesis utilization, including anthropometric and demographic data.

Data management and analysis utilizes a secure network and computer system to protect confidential data with security measures established by the HIPAA Security Rules. The data collected are verified, edited, and updated to provide clean data for analysis. Once data pass all the edit procedures, analytical data sets will be created for analysis by a statistician. As a final step in quality control and an initial step in analysis, descriptive statistics will be calculated and graphic displays created.

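### Current PCM-liner users are not excluded, and for such a subject the protocol's definitions of the control liner conflict

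*Combined protocol and SAP*

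**What the plan says.** **Eligibility (Subjects paragraph).** On the current device the protocol requires: "Inclusion criteria are the use of a prosthesis with liner suspension, at least one year of prosthesis use, a well-fitting socket". The exclusions begin: "Exclusion criteria are use of a non-standard liner size, known allergies against liner materials, and any inability to understand the protocol". No criterion mentions the material of the current liner.

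**Liner issued at entry (Methods, text after Table 1).** "The liner material is either the same as in their existing liner or PCM infused silicon, depending on group allocation".

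**Control condition elsewhere.**
- Methods, design paragraph: "the members of the other group are fitted with regular gel or silicone liners", and at the crossover "After six months, the first group receives conventional liners (and turn their PCM liners in) and the second group receives PCM liners".
- Table 1: the condition listed alongside the PCM liner is called a placebo liner.
- Methods, text after Table 1, on serial numbers: the number is "the only sign by which it can be identified as a PCM or conventional liner".
- Methods, six-month appointment: "subjects turn in their two study liners and receive two new liners, representing the respectively other variety".

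**Entry data (Methods, first appointment).** Liner size, height, weight, age and time since limb loss are recorded. Existing liner material is not listed.

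**The concern.** The entry rule takes the subject's existing material as the control. That works only if the existing liner is not PCM, and the criteria do not ensure this. For a current PCM user there are two outcomes, and the text does not say which applies.

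- If the entry rule governs, a control-first subject wears PCM in both half-years. Such a subject has a true liner difference of zero and pulls the pooled effect towards zero.
- If the conventional-liner descriptions govern, the subject does have a contrast but enters already used to the active product. Someone who knows how PCM feels may be able to tell which half-year is which. That bears most on the PEQ ratings, which are self-reported.

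The plan states no check that would show the first case before analysis. The serial-number list is opened only after analysis is complete, and existing material is not among the listed entry data.

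**Working it through.** **1. The passages applied to a current PCM user**

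| Sequence | Entry rule read literally | Design paragraph, Table 1, six-month text |
|---|---|---|
| Control first | PCM, then PCM: no contrast | Conventional, then PCM |
| PCM first | PCM at entry; the rule is written for entry, and the design paragraph then gives conventional | PCM, then conventional |

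The zero-contrast result therefore follows directly only for the control-first sequence, about half of such subjects under balanced allocation.

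**2. The plan's own power figure**

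Inputs from the Subjects paragraph: effect size d = 0.47, N = 50, one-sided, stated power 85%; 9 dropouts leave 50 − 9 = 41, stated power 80%. Alpha is not given; 5% is assumed here. The method is a paired t-test with noncentrality d√N and N − 1 degrees of freedom.

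- d = 0.47, one-sided: 94.9% (N = 50), 90.5% (N = 41).
- d = 0.47, two-sided: 90.3% and 83.6%.
- d = 4/10 = 0.40 (the four-day difference over the 10-day SD), one-sided: 87.4% and 80.9%.

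The stated 85% is not reproduced. That is a separate matter. The figures below show the size of a loss, not the plan's actual power.

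**3. Dilution if a share f of subjects has zero contrast**

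The share f is an assumption, because the documents give none. With these subjects kept in the analysis and the same within-group SD of the difference, the mean is (1 − f)d and the mixture adds variance f(1 − f)d²:

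d_eff = (1 − f)d / √(1 + f(1 − f)d²)

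For f = 5/50 = 0.10 and d = 0.47: 0.423 / √(1 + 0.09 × 0.2209) = 0.423 / 1.0099 = 0.419.

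One-sided 5% power:

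| f | d = 0.47, N = 50 | d = 0.47, N = 41 | d = 0.40, N = 50 | d = 0.40, N = 41 |
|---|---|---|---|---|
| 0 | 94.9% | 90.5% | 87.4% | 80.9% |
| 0.05 | 92.7% | 87.5% | 84.0% | 77.0% |
| 0.10 | 89.9% | 83.9% | 80.2% | 72.7% |
| 0.20 | 82.4% | 75.2% | 71.2% | 63.5% |

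If 10% of subjects are PCM users but only the control-first half lose the contrast, the f = 0.05 row applies. At d = 0.47 and N = 50 the loss is then 94.9 − 92.7 = 2.2 points rather than 94.9 − 89.9 = 5.0 points.

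**4. Blinding**

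No arithmetic applies. The documents give no data on whether users can tell the materials apart.

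**The case against.** A reader might infer that the protocol puts the active treatment into the control arm and gives PCM users PCM in both half-years. The documents do not support that as the settled plan. The design paragraph, Table 1, the serial-number sentence and the six-month instruction all treat the control as something other than PCM. The entry rule itself sets existing material against PCM, which suggests that its authors had a non-PCM liner in mind. Even read literally, it removes the contrast directly only for control-first subjects. This objection stands: double PCM is one reading of conflicting text.

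It is also fair to say that no passage shows that any PCM user would enrol. At d = 0.47 and N = 50, five zero-contrast subjects still leave 89.9%, above the stated 85%. The power figures are therefore illustrations only.

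The blinding risk is plausible but not shown. Colour and outer fabric are uniform, and any subject can compare a study liner with a familiar one. Self-reported days count only where the step data agree, which limits bias by that route. The PEQ ratings have no such cross-check.

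Nor can one say that a PCM-versus-PCM subject would certainly go unnoticed. Liners are custom ordered, and matching material means that someone must know it, so ordering records might reveal the case. What can be said is that the plan states no such check.

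None of this closes the gap. The criteria are silent, and no passage says which control definition governs a current PCM user.

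**Conclusion.** The point holds as a gap in eligibility joined to an internal contradiction. Current PCM users may enrol, and the protocol gives incompatible definitions of their control liner. One definition removes the contrast for control-first subjects; the other keeps it but has them enter on the active product, with a possible cost to the blind.

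The size depends on an unknown share of PCM users. With none, nothing is lost. With 5 of 50 at zero contrast, power at d = 0.47 falls by about 5 points, and by about half that if only control-first subjects are affected. These figures assume one-sided 5%, a paired analysis, and an equal SD of the difference in affected and unaffected subjects. The correction is worth making because it is cheap and specific, not because a large loss has been shown.

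**What to change.** 1. Add current use of a PCM (temperature-control) liner to the exclusion criteria in the Subjects paragraph. The documents offer no basis for choosing a look-back period for past use.
2. Reword the entry rule after Table 1 so that the control is a conventional non-PCM liner, consistent with the design paragraph, Table 1 and the six-month text.
3. Add existing liner material to the data recorded at the first appointment.
4. If any PCM user is already enrolled, report the main comparison with and without them. Ordering records may identify them where material was not recorded.

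The cost is two wording changes, one data field and a slightly smaller recruitment pool. For scale, at d = 0.47 and one-sided 5%, leaving out 5 of 50 subjects without replacing them gives 92.8% power with 45, against 89.9% if the same 5 stay in with zero contrast.
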